2 STUDY SYNOPSIS

Study Objective

The purpose of this research study is to evaluate the clinical outcomes of the use of low-energy segment removal with a micro-interventional irrigation/aspiration port (MICOR-304) to evacuate the lens prior to intraocular lens insertion in subjects undergoing routine cataract surgery.

Study Population

Only 1 eye per subject will be enrolled into the study. Up to 100 subjects (100 eyes) will be enrolled into the first phase of the study and an additional 200 subjects (200 eyes) will be enrolled in the second phase of the study, for a total of 300 subjects (300 eyes). Subjects will be enrolled in one of the two cohorts of this clinical investigation. For the first 100 eyes enrolled – up to 75 eyes may be enrolled in Cohort 1 and up to 75 eyes in Cohort 2. For the additional second phase of 200 eyes – up 150 eyes may be enrolled in Cohort 1 and up to 150 eyes in Cohort 2. Overall, for the 300-study eye investigation, there should be no more than 225 eyes in either Cohort 1 or 2.

Study Design

This is multicenter, multi-cohort, prospective clinical study designed to provide longitudinal, observational, non-comparative clinical outcome data for mechanical non-phacoemulsification lens extraction using low-energy segment removal with a micro-interventional irrigation/aspiration port (MICOR-304) to evacuate the lens prior to intraocular lens insertion.

Subjects will be stratified into two Cohorts. Cohort 1 is comprised of eyes with mild-to-moderate cataracts only (Grade 1 to 2). Cohort 2 is comprised of eyes with moderate to more dense cataracts only (Grade 2+ to 3+).

Inclusion Criteria

1. Able to understand study requirements, willing to follow study instructions and willing to return for required study follow-up visits.
2. Willing and able to understand and complete the informed consent document
3. Subjects with a cataract grade of 1 to 3+ and are scheduled to undergo cataract surgery
4. Subjects \geq 18 years of age

5. Clear intraocular media, other than cataract

Exclusion Criteria for both Cohorts

1. Polar cataracts
2. Zonular instability
3. Subjects who have been diagnosed with dry eye which has been untreated and or would affect postoperative visual acuity outcomes (i.e., if the subject has had dry eye treatments / devices and has, or is undergoing treatment and deemed to be stable, they would be an eligible study candidate).

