7 STUDY PROCEDURES

Subject Entry

Participants who meet the inclusion and exclusion will be asked to enroll in the study. The investigator or designee will explain the study purpose, procedures and responsibilities to the potential participant and provide sufficient opportunity to ask questions, while allowing adequate time for consideration of the information provided. Upon participant confirmation of interest, written informed consent will be obtained and the subject will be enrolled in the study. One copy of the informed consent document (ICD) will be retained with the subject's medical records and one copy will be provided to the subject.

Subject Cohort Selection:

Subjects with mild to moderate cataracts (Grade 1-2) who meet the inclusion criteria, will be assigned to Cohort 1. Subjects with severe cataracts (Grade 2+ - 3+) meeting the inclusion criteria will be assigned to cohort 2. Subjects with intermediate cataracts, which may qualify for either Cohort, will be assigned based on investigator discretion and clinical judgement since exact lens density judgment is impossible to determine prior to surgery.

Only 1 eye per subject will be enrolled into the study. Up to 100 subjects (100 eyes) will be enrolled into the first phase of the study and an additional 200 subjects (200 eyes) will be enrolled in the second phase of the study, for a total of 300 subjects (300 eyes). Subjects will

be enrolled in one of the two cohorts of this clinical investigation. For the first 100 eyes enrolled – up to 75 eyes in Cohort 1 and up to 75 eyes in Cohort 2. For the additional second phase of 200 eyes – up to 150 eyes per subject in Cohort 1 and up to 150 eyes in Cohort 2. Overall, for the 300 study eye investigation, there should be no more than 225 eyes in either Cohort 1 or 2.

Surgical Procedure

All subjects will undergo routine cataract surgical intervention with IOL implantation. All subjects will receive the standard of care preoperative and peri-operative medications and assessments. The procedure can be performed under either topical or peri/retrobulbar anesthesia per investigator discretion. Clear cornea cataract surgery will be performed with the following steps:

Study Eye

For each subject, one or both eyes may be treated; however, if both eyes are scheduled for treatment, then one eye will be designated as the “study eye” based on investigator discretion prior to any surgical intervention.

Study Visits

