8 STATISTICAL METHODS

Analysis Plan

Primary and secondary endpoints will be analyzed with descriptive statistics. Point estimates and confidence intervals will be calculated for each outcome. 95% confidence intervals for lens removal time and irrigation fluid volume will be calculated based on a t distribution.

Frequency tabulations of safety outcomes will be made at the 1 week and 1-month follow-up evaluations.

Sample Size

The sample size for this study is based on the following:

For safety, the pooled sample of 100 eyes will have a greater than 90% chance of detecting one or more rare adverse events, i.e., those with an expected rate of occurrence of 2.5%.

We anticipate that for Cohort 1 (grades 1 – 2) the mean lens removal time will be approximately 5 minutes, with standard deviation of 1 minute, and for Cohort 2 (grades 2+) the mean lens removal time will be about 10 minutes, with standard deviation 2 minutes. Under

these assumptions a sample of 50 eyes will produce a confidence interval width of approximately 0.56 minutes for Cohort 1 and 1.14 minutes for Cohort 2.

For Irrigation Fluid Volume we anticipate a mean of 30ml with a standard deviation of approximately 5ml for both Cohorts. Under these assumptions, a sample of 50 eyes will produce a confidence interval width of approximately 2.8ml for each Cohort.

Adverse Events

The number of subjects reporting at least 1 AE of a given type will be summarized. AEs not listed that occur during the study will be added to the summary of AEs. Summaries will also be provided for AEs considered to be related to the device. Each AE will be summarized by incidence and percentage.

Central Corneal Pachymetry

Central corneal pachymetry data will be summarized with N, mean, standard deviation, minima, median, and maxima. A 95% confidence interval will be provided for the change and percentage change from baseline. Change between two consecutive visits will also be summarized.

Slit Lamp and Fundus Exam Findings

Slit lamp, and fundus examination findings at scheduled follow-up visits will be tabulated such that the number and percentage of subjects in each category will be summarized.

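### Section 8 bases the sample size on 100 pooled eyes and 50 per cohort, but 300 eyes are planned; the Cohort 1 width of 0.56 min should read 0.57

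*Combined protocol and SAP*

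**What the plan says.** Section 8 (Statistical Methods, Sample Size) opens with "The sample size for this study is based on the following". Three statements follow.

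- Safety: "For safety, the pooled sample of 100 eyes will have a greater than 90% chance of detecting one or more rare adverse events", for events with an assumed rate of 2.5%.
- Lens removal time: with standard deviations of 1 minute (Cohort 1) and 2 minutes (Cohort 2), "a sample of 50 eyes will produce a confidence interval width of approximately 0.56 minutes for Cohort 1", and 1.14 minutes for Cohort 2.
- Irrigation volume: with a standard deviation of about 5 ml in both cohorts, "a sample of 50 eyes will produce a confidence interval width of approximately 2.8ml for each Cohort".

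The Analysis Plan in the same section fixes the interval method: "95% confidence intervals for lens removal time and irrigation fluid volume will be calculated based on a t distribution".

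The enrolment plan is in Section 2 (Study Population) and Section 7 (Subject Cohort Selection). After a first phase of up to 100 eyes, "an additional 200 subjects (200 eyes) will be enrolled in the second phase of the study", "for a total of 300 subjects (300 eyes"). The cohort caps are 75 eyes in the first phase and 150 in the second. Overall, "there should be no more than 225 eyes in either Cohort 1 or 2". Section 8 mentions neither the phases nor the figures 200 and 300.

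**The concern.** The study has no hypothesis test and no success criterion. The detection chance and the interval widths are therefore the only quantitative design properties that the protocol states. They are worded as properties of the study as a whole, yet they belong to 100 eyes in total and 50 per cohort. Pooling both cohorts under the current plan gives 300 eyes, not 100.

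A reader who takes Section 8 at face value gets the wrong sensitivity to rare events and the wrong precision for both primary efficacy measures, and cannot tell whether the figures are meant for the first phase or for the whole study. What is at stake is the accuracy of the stated design, not the conduct or the results.

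One printed width also disagrees with its neighbour. At equal n, doubling the standard deviation doubles the width, so the two lens-time widths must stand in the ratio 1:2. The figures 0.56 and 1.14 do not.

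**Working it through.** **Inputs.** From Section 8: event rate 2.5%; standard deviations 1 min, 2 min and 5 ml; 95% t intervals; n = 100 pooled and 50 per cohort. From Sections 2 and 7: 300 eyes in total; caps of 75 (first phase), 150 (second phase) and 225 (overall) per cohort.

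**Formulas.** Eyes are taken as independent and evaluable.

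- Chance of at least one event: 1 − (1 − p)^n.
- Event rate at which that chance is 90%: 1 − 0.1^(1/n).
- Full interval width: 2 × t(0.975, n − 1) × SD / √n.

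**Step 1: the plan's own figures.**

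- Safety, n = 100: 1 − 0.975^100 = 0.9205, which agrees with the claim of more than 90%.
- Widths, n = 50, t(0.975, 49) = 2.010: 2 × 2.010 × 1 / √50 = 0.568 min for Cohort 1. Twice that is 1.137 min for Cohort 2, and five times 0.568 is 2.842 ml for volume.

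The stated 1.14 min and 2.8 ml are reproduced. The stated 0.56 min is not: 0.568 rounds to 0.57.

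**Step 2: can 0.56 and 1.14 both be right after rounding?** A value that rounds to 0.56 lies between 0.555 and 0.565. Twice that is 1.11 to 1.13. A value that rounds to 1.14 is at least 1.135. The two ranges do not meet. A normal quantile does not rescue 0.56 either: it gives 0.554 and 1.109.

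**Step 3: safety at the planned total.**

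- n = 300, p = 0.025: 1 − 0.975^300 = 0.9995, or 99.95%.
- Rate detected with 90% chance: 1 − 0.1^(1/100) = 2.28% at 100 eyes, and 1 − 0.1^(1/300) = 0.765% at 300. The latter is rounded up to 0.77%, because 0.77% gives 90.2% and 0.76% gives 89.9%.

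**Step 4: cohort sizes that the caps allow.** If all 300 eyes are enrolled, the smaller cohort has at least 300 − 225 = 75 eyes. The phase caps give the same: at least (100 − 75) + (200 − 150) = 25 + 50 = 75. If all 100 first-phase eyes are enrolled, a split as uneven as 25/75 is allowed.

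**Step 5: widths by cohort size.**

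| Eyes in cohort | Cohort 1 time (SD 1 min) | Cohort 2 time (SD 2 min) | Volume (SD 5 ml) |
|---|---|---|---|
| 25 | 0.826 min | 1.651 min | 4.128 ml |
| 50 | 0.568 min | 1.137 min | 2.842 ml |
| 75 | 0.460 min | 0.920 min | 2.301 ml |
| 150 | 0.323 min | 0.645 min | 1.613 ml |
| 225 | 0.263 min | 0.525 min | 1.314 ml |

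**Step 6: the cohorts trade off.** With 300 eyes in total, 225 in one cohort leaves 75 in the other.

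- 225 in Cohort 1 and 75 in Cohort 2: 0.26 and 0.92 min; 1.3 and 2.3 ml.
- 75 in Cohort 1 and 225 in Cohort 2: 0.46 and 0.53 min; 2.3 and 1.3 ml.
- 150 in each: 0.32 and 0.65 min; 1.6 ml in each.

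The two best widths cannot occur together, nor can the two worst.

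**The case against.** The strongest reply is that nothing depends on this. The study is descriptive and non-comparative, and more eyes can only help. At full enrolment each cohort has at least 75 eyes, so under the protocol's standard deviations the 50-eye widths are upper bounds, and the detection chance is higher than stated. The 100 eyes in Section 8 match the first phase in Sections 2 and 7, and a reader has the inputs needed to rescale. All of this stands, and it is why the point is minor. It does not make the text right: Section 8 presents the figures as the basis for the study and does not label them as first-phase figures.

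On 0.56 against 0.57, the reply is that the protocol says approximately and that the gap is 0.008 min, about half a second. The size is indeed trivial. But the two printed widths cannot both be right, and correcting one digit costs nothing.

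Three stronger readings are tempting, and the documents support none of them.

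- A reader might infer that the study is too small. The reverse holds: the planned sample is three times the one described.
- A reader might infer that the additional 200 eyes have no rationale. No visible text gives one, but pages were removed and Appendix 2 is redacted, so its absence cannot be asserted. A stated reason would be useful documentation, and its lack is not an error.
- A reader might infer that similarity of eyes within a site could cancel the gain in precision. The documents give no intra-site correlation. Setting a larger clustered sample against a smaller independent one is also not a like-for-like comparison.

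**Conclusion.** The point holds as a minor one: Section 8 is wrong as written. Its detection chance and widths are right, apart from one digit, for 100 pooled eyes and 50 per cohort, but they do not describe the 300-eye study that it claims to size.

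The largest understatement concerns rare events: the rate detectable with 90% chance is 2.28% as described and about 0.77% as planned, roughly a threefold difference. With an even split of 300, the interval widths are a little under 60% of those stated (0.323 / 0.568 = 0.57).

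These figures rest on the protocol's own standard deviations, on independent and evaluable eyes, and on full enrolment of 300. The range of 75 to 225 eyes per cohort is derived from the caps and is not a required minimum. The mismatch is conservative only at full enrolment. In the first phase taken alone, the caps allow a cohort of 25 eyes, and its widths would exceed those stated.

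**What to change.** Revise the Sample Size text in Section 8.

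1. Label the present figures as applying to 100 pooled eyes and 50 eyes per cohort, and change the Cohort 1 width from 0.56 to 0.57 min. Do not describe an even split as planned. The first-phase caps allow 25/75, and 25 eyes give 0.83 min (Cohort 1), 1.65 min (Cohort 2) or 4.1 ml (volume).
2. Add the figures for the planned total, for example: Assuming 300 evaluable, independent eyes, the chance of at least one AE is 99.95% at a true rate of 2.5% and 90% at a true rate of about 0.77%. With 150 eyes per cohort, the 95% t-interval widths are 0.32 min (Cohort 1), 0.65 min (Cohort 2) and 1.6 ml (volume). At the caps the cohorts trade off: 225 eyes in Cohort 1 and 75 in Cohort 2 give 0.26 and 0.92 min (1.3 and 2.3 ml), and the reverse split gives 0.46 and 0.53 min (2.3 and 1.3 ml).
3. Optionally, have the sponsor state its reason for the additional 200 eyes. Figures computed after the total was chosen do not supply that reason.

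The cost is wording in one section. Enrolment, endpoints and analyses do not change.

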9 ADVERSE EVENTS

All ocular AEs in the study eye must be reported on the relevant CRF. AEs will be categorized by degree of harm to the subject (mild, moderate, or severe).

Ocular conditions or diseases present at the time of study enrollment will be considered as “baseline”. Changes in a chronic condition or disease that are consistent with natural disease progression are not considered AEs.

AEs that might reasonably be expected to occur include, but are not limited to, the following:

- Anterior chamber cell and flare requiring initiation of steroid treatment

- Capsular tear and rupture
- Vitreous loss
- Endophthalmitis
- Corneal edema
- Retinal tear / detachment
- Dialysis, flap tears or proliferative vitreoretinopathy
- Cystoid Macular Edema
- Hypopyon
- Hyphema
- Lens dislocation
- Pupillary block
- Acute corneal decompensation
- Raised IOP requiring treatment
- Severe inflammation
- Secondary Surgical Intervention

Grading of Adverse Events

AEs will be graded on a 3-point scale (mild, moderate, severe) using the following definitions:

- Mild: Discomfort noticed, but there is no disruption of normal daily activity
- Moderate: Discomfort is sufficient to reduce or affect normal daily activity
- Severe: Subject is incapacitated as evidenced by the inability to work or perform normal daily activity

Follow-up of Adverse Events

AEs will be followed until resolution or stabilization of the event.

Expedited Reporting of Adverse Events

An AE should be classified as SERIOUS if it:

- Caused or led to death.
- Was life threatening (i.e., the AE placed the subject at immediate risk of death).
- Required or prolonged inpatient hospitalization (i.e., the AE required at least a 24-hour inpatient hospitalization or prolonged a hospitalization beyond the expected length of stay).
- Was sight threatening.

- Was disabling (i.e., the AE resulted in a substantial disruption of the subject's ability to carry out normal life functions).
- Resulted in a congenital anomaly/birth defect (i.e., an adverse outcome in a child or fetus of a subject due to participation in this study).
- Does not meet any of the above serious criteria but jeopardized the subject by requiring medical or surgical intervention to prevent one of the outcomes listed above.

Serious events or serious device related adverse events should be reported in accordance with the following requirements:

Event Type	Reporting Timeframe
Serious device related adverse event	Within 24 hours of becoming aware of the event
SAE	Within 1 week of becoming aware of the event

Any ocular-related serious adverse event (SAE) should be reported to the study sponsor WITHIN ONE WORKING DAY of learning of the event. Non-ocular-related SAEs should be reported to the study sponsor within TWO WORKING DAYS of learning of the event. Email the Adverse Event CRF to [contact]

Any serious device related adverse events must be reported to the following three entities:

1. The study sponsor – Within ONE WORKING DAY of the investigator first learning of the event, email the AE CRF to [contact]; and
2. The reviewing Institutional Review Board(IRB) Committee – As soon as possible, but no later than 7 working days after the investigator first learns of the event, report per the IRB instructions.
3. FDA under the reporting requirements for 21 CFR Part 803 Medical Device Reporting

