4. Concurrent participation or participation in any clinical trial up to 30 days prior to preoperative visit.
5. Subjects that are pregnant, lactating or planning to become pregnant during the course of the study

Primary Endpoint

Efficacy: Total lens removal time and amount of irrigation solution fluid volume used during the surgical procedure.

- Total lens removal time is defined in two phases:
 - The beginning time starts when the surgeon enters into the eye with the MICOR-304 to start the lens removal process and completing when the surgeon finishes the nucleus lens removal with the MICOR-304 before changing over to irrigation and aspiration.
 - The second phase of lens removal time is the irrigation and aspiration stage for cortex removal which starts when the irrigation and aspiration tip enters the eye and completion time is when the cortex is removed.
- Total irrigation solution volume will be recorded using the indicators on the waste bag which will have labels that have pre-defined markers to indicate milliliters (ml) of volume of irrigation solution used for the surgical procedure.

Safety: Rate of occurrence of intraoperative and postoperative adverse events (AEs)

Secondary Endpoints

- UCVA on day 1
- BCVA on days 7, 30
- Change in corneal thickness from baseline through Day 30
- Rate of occurrence of intraoperative and postoperative adverse events (AE)
- Results of slit lamp and fundus examinations, which are not considered to be AEs

- Total procedure time: defined as the beginning time when the surgeon makes the first incision in the eye and completion time is when the eye speculum is removed at the end of the procedure.

Schedule of Visits

Screening visit, intraoperative visit, post-operative day 1, day 7, day 30.

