6. STUDY POPULATION

Individuals will be assessed for study eligibility based on the criteria presented below:

Inclusion Criteria

1. Able to understand study requirements, willing to follow study instructions and willing to return for required study follow-up visits
2. Willing and able to understand and complete the informed consent document
3. Subjects with a cataract grade of 1 to 3+ and are scheduled to undergo cataract surgery
4. Subjects \geq 18 years of age
5. Clear intraocular media, other than cataract

Exclusion Criteria for both Cohorts

1. Polar cataracts
2. Zonular instability
3. Subjects who have been diagnosed with dry eye which has been untreated and or would affect postoperative visual acuity outcomes (i.e., if the subject has had dry eye treatments / devices and has, or is undergoing treatment and deemed to be stable, they would be an eligible study).
4. Concurrent participation or participation in any clinical trial up to 30 days prior to preoperative visit
5. Subjects that are pregnant, lactating or planning to become pregnant during the course of the study

Primary Endpoints

Efficacy: Total lens removal time and amount of irrigation solution fluid volume used during the surgical procedure.

- Total lens removal time is defined in two phases:
 - The beginning time starts when the surgeon enters the eye with the MICOR-304 to start the lens removal process and completing when the surgeon finishes the nucleus lens removal with the MICOR-304 before changing over to irrigation and aspiration.
 - The second phase of lens removal time is the irrigation and aspiration stage for cortex removal which starts when the irrigation and aspiration tip enters the eye and completion time is when the cortex is removed.
- Total irrigation solution volume will be recorded using the indicators on the waste bag which will have labels that have pre-defined markers to indicate milliliters (ml) of volume of irrigation solution used for the surgical procedure.

Safety: Rate of occurrence of intraoperative and postoperative adverse events (AE)

Secondary Endpoints

- UCVA on day 1,7,30
- Change in corneal thickness from baseline through Day 30
- Rate of occurrence of intraoperative and postoperative adverse events (AE)
- Results of slit lamp and fundus examinations, which are not considered to be AEs

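### The cell-and-flare adverse event is triggered by starting a steroid, so if eyes are already on one, the count for this AE type can be too low and can vary by site

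*Combined protocol and SAP*

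**What the plan says.** - **The listed event.** Section 9 includes "Anterior chamber cell and flare requiring initiation of steroid treatment" among the expected AEs. The same list has "Severe inflammation" and hypopyon, neither with a steroid condition.
- **Status of the list.** It is open: "AEs that might reasonably be expected to occur include, but are not limited to, the following". The general rule comes before it: "All ocular AEs in the study eye must be reported on the relevant CRF".
- **Analysis.** Section 8 summarises AEs by type and states: "AEs not listed that occur during the study will be added to the summary of AEs".
- **Background medication.** Section 7, Surgical Procedure: "All subjects will receive the standard of care preoperative and peri-operative medications and assessments". No drug is named. Section 5 plans up to 10 sites.
- **Endpoints.** The occurrence rate of intraoperative and postoperative AEs is the primary safety endpoint (Synopsis and Section 6). Slit lamp and fundus results not considered AEs form a separate secondary endpoint, and Section 8 tabulates slit lamp findings by category at scheduled follow-up visits.
- **Medication records.** Appendix 1 marks ocular medications at every visit, including day 0. The intraoperative list in Section 7 omits them.

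**The concern.** The trigger for this item is a treatment decision, and specifically a first one. Whether that decision can occur depends on what the eye is already receiving. Take two eyes with the same cell and flare at the one-week visit. In an eye on no steroid, starting one meets the item. In an eye already on one, increasing or prolonging it does not.

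For such eyes a literal reading can only remove events, so any error lowers the reported inflammation count. Postoperative inflammation is a plausible effect of a lens-removal device, and the study has no comparator arm in which the same loss would occur. At stake is whether the count for this AE type describes the device or partly describes background medication.

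**Working it through.** **1. The path of one eye through the text.** Suppose an eye is on a routine steroid and has cell and flare that leads to more or longer steroid.

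- *Listed item:* not met on a literal reading, because nothing is initiated. The visible text has no rule for an increase, extension or restart. The raised-IOP item in the same list asks only that treatment be required, so the narrower trigger is particular to cell and flare.
- *"Severe inflammation":* no cell or flare threshold is visible. Section 9 defines severe only for AE grading, by incapacity in daily activity. Inflammation below severe is not caught here.
- *Hypopyon:* caught only if that sign is present.
- *General rule on ocular AEs:* catches the eye if the investigator regards the finding as an AE. The visible text gives no general AE definition, so for cell and flare below severe the steroid qualifier is the only stated divider.
- *Slit lamp endpoint:* available as a non-AE destination. A finding recorded only there does not enter the AE rate.

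The eye can therefore be recorded as an AE or as a slit lamp finding, and the stated trigger points to the second.

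**2. The plan's own safety figure.** Section 8 states a greater than 90% chance of seeing at least one event of a type with a 2.5% rate in 100 eyes. Check: 1 − (1 − 0.025)^100 = 1 − 0.975^100 = 0.9205. The figure reproduces and does not depend on the AE wording.

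**3. Illustration of sensitivity, for this AE type only.** Let f be the share of true events of this type that go uncounted because the eye was already on steroid. The documents give no value for f, so the full range is shown. They also give no rate for this event, so the plan's 2.5% is borrowed.

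Counted rate = 0.025 × (1 − f). Chance of at least one counted event in n eyes = 1 − [1 − 0.025 × (1 − f)]^n. Expected count in 300 eyes = 300 × 0.025 × (1 − f).

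| f | Counted rate | At least one in 100 eyes | At least one in 300 eyes | Expected count in 300 eyes |
|---|---|---|---|---|
| 0 | 2.5% | 92.0% | 99.9% | 7.5 |
| 0.25 | 1.875% | 84.9% | 99.7% | 5.6 |
| 0.5 | 1.25% | 71.6% | 97.7% | 3.75 |
| 0.75 | 0.625% | 46.6% | 84.8% | 1.9 |
| 0.9 | 0.25% | 22.1% | 52.8% | 0.75 |
| 1 | 0% | 0% | 0% | 0 |

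f is at most the share of events in eyes whose steroid is only increased or prolonged, and it falls with every such eye reported under the general rule. If all are reported, f = 0.

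**The case against.** The strongest reply is that the list illustrates expected events and does not set the counting rule. Every ocular AE in the study eye must be reported, listed or not, and unlisted AEs join the summary. An investigator who sees marked cell and flare in an eye on steroid is obliged to report it if it is an AE. This stands, and it prevents any claim that the plan excludes such eyes. It does not settle the point, because the duty begins only once the finding is judged to be an AE, and for cell and flare below severe the only visible criterion is the steroid trigger.

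Three further objections also stand:

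- **Routine steroid is not documented.** Section 7 refers to preoperative and peri-operative medication, names no drug and does not mention postoperative use. If no eye is on a steroid, the problem does not arise.
- **The visible text is incomplete.** The surgical steps in Section 7 are absent and Appendix 2 is redacted, so a grading scale may exist. A scale alone would not alter the trigger in Section 9.
- **A partial check exists.** Slit lamp findings and ocular medications are recorded at every postoperative visit, so missed eyes could be looked for. The plan does not say that these records will be used to classify events.

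A reader might infer that inflammation counts only when a steroid is started. The documents do not support that, given "Severe inflammation", hypopyon and the open list.

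**Conclusion.** The point holds as a wording gap in one component of the primary safety endpoint. Where an eye is already on steroid, the stated trigger does not literally cover cell and flare managed by increasing or prolonging it. The count for this AE type can then be too low, and can vary with site practice. Among such eyes the literal reading loses events and adds none.

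The size cannot be estimated from the documents. The table shows sensitivity under an assumed loss share and a borrowed event rate; it is not a forecast.

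A reader might go further and infer that the primary safety rate as a whole reflects the sites' medication rather than the device. The documents do not support this. The wording touches one of 16 listed types, other routes to reporting remain open, and the descriptive analysis has no safety threshold or test that this item could tip. The conclusion rests on two assumptions: that some eyes are on a routine steroid, and that some investigators follow the qualifier literally.

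**What to change.** - Reword the counted event in Section 9 as: *Anterior chamber cell and flare for which steroid was started, increased or prolonged beyond the regimen planned for that eye at surgery.*
- Record each eye's planned regimen at surgery in the ocular medications field. Appendix 1 marks this field on day 0 and the intraoperative list in Section 7 omits it, so the two should be reconciled.
- Report this AE type beside the slit lamp cell-and-flare tabulation. Entry into that tabulation does not depend on a treatment decision, so a reader can see how many eyes had the finding and how many were counted as AEs. If the slit lamp categories do not already separate cell and flare (Appendix 2 is redacted), they would need to.

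This changes how events are counted and changes no treatment; each eye's regimen stays as it is. The cost is one reworded term, one entry in an existing field and one paired table. The inflammation rate may come out higher. Some dependence on the planned regimen remains, because an eye with a longer or heavier planned course crosses the new line less readily. The paired slit lamp table is there for that reason.
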